9.0 DATA COLLECTION AND REPORTING

9.1 Collection and Review

9.1.1 Record all data according to SOP-QC-030, Data Generation and Review. Raw data or copies of data (marked as such with location of original data indicated) must be included in the validation package.

9.1.2 All data generated during execution of the validation protocol will be reviewed for completeness and accuracy in accordance with SOP-QC-030, Data Generation and Review.

9.2 Reporting

9.2.1 Collate the results of the executed validation protocol, including all associated data, in a verification report.

9.2.1.1 The report must be approved by the same individuals who approved the associated validation protocol(s).

9.2.2 Each completed validation package shall contain all relevant approved protocols, supporting data and reports.

9.2.3 Verification packages are controlled and archived by Document Control in accordance with SOP-QA-020, Quality Records.

10.0 NONCONFORMANCE

Document nonconformances according to SOP-QA-014, Handling and Control of Nonconformances.

12.0 REVISION HISTORY

| Revision Level | Brief Description of Revision(s) | Effective Date |
|----------------|----------------------------------|---------------------------------|
| 00 | Initial Document | See first page of this document |

PRO: ABCA2 GIRMS Analytical Validation Clinical Performance Study – Patient Sample Collection
EXHIBIT C: PRO-QC-191, ABCA2 GIRMS Analytical Validation – Bias and Total Analytical Error

8 Pages

20.0 EXHIBIT C. PRO-QC-191.00, ABCA2 GIRMS ANALYTICAL VALIDATION – BIAS AND TOTAL ANALYTICAL ERROR

UNCONTROLLED COPY
Version May Not Be Current

Effective Date: SEP 03 2020

1.0 PURPOSE

The purpose of this bias and total analytical error analytical validation study is to establish documented evidence toward the safety and effectiveness of the ABCA2 GIRMS system to be used to determine the carbon stable isotope ratio (expressed as $\delta^{13}\text{C}$) of CO_2 in breath samples collected during administration of Cairn's Gastric Emptying Breath Test (GEBT).

2.0 BACKGROUND

The performance characteristics of the ABCA GIRMS instrument currently in use for analyzing carbon stable isotope ratios of CO_2 in breath samples collected during administration of the GEBT were established and documented in PRO-QC-114.01, Analytical Performance of ABCA GIRMS Instruments, and the associated report (submitted as part of PMA P110015).

This protocol includes studies that seek to confirm an acceptable level of bias and total analytical error of the ABCA2 GIRMS system and demonstrate comparable performance characteristics to the original ABCA GIRMS system. This study will be performed in accordance with CLSI Guidance EP09c, "Measurement Procedure Comparison and Bias Estimation Using Patient Samples"; 3rd edition; June 2018, EP21- "Evaluation of Total Analytical Error for Quantitative Medical Laboratory Measurement Procedures – 2nd Edition"; July 2016 and Assay Migration Studies for In Vitro Diagnostic Devices – Guidance for Industry and FDA Staff.

3.0 RESPONSIBILITIES

| Requirement | Responsibility |
|---------------------|--|
| Protocol generation | Data Management Associate |
| Protocol approval | Director of Quality Assurance and Regulatory Compliance, Clinical Laboratory Director, Chief Information and Instrumentation Officer |
| Protocol execution | Clinical Laboratory personnel, Data Management Associate, Chief Information and Instrumentation Officer |

| Originator: | NAME (Print) | SIGNATURE | DATE |
|--------------|--------------------|--|----------|
| Originator: | [name] |  | 9/2/2020 |
| Approved By: | [name] |  | 9/2/2020 |
| Approved By: | [name] |  | 9-2-2020 |
| Approved By: | See Attached | | 09-3-20 |

Effective Date:**1.0 PURPOSE**

The purpose of this bias and total analytical error analytical validation study is to establish documented evidence toward the safety and effectiveness of the ABCA2 GIRMS system to be used to determine the carbon stable isotope ratio (expressed as $\delta^{13}\text{C}$) of CO_2 in breath samples collected during administration of Cairn's Gastric Emptying Breath Test (GEBT).

2.0 BACKGROUND

The performance characteristics of the ABCA GIRMS instrument currently in use for analyzing carbon stable isotope ratios of CO_2 in breath samples collected during administration of the GEBT were established and documented in PRO-QC-114.01, Analytical Performance of ABCA GIRMS Instruments, and the associated report (submitted as part of PMA P110015).

This protocol includes studies that seek to confirm an acceptable level of bias and total analytical error of the ABCA2 GIRMS system and demonstrate comparable performance characteristics to the original ABCA GIRMS system. This study will be performed in accordance with CLSI Guidance EP09c, "Measurement Procedure Comparison and Bias Estimation Using Patient Samples"; 3rd edition; June 2018, EP21- "Evaluation of Total Analytical Error for Quantitative Medical Laboratory Measurement Procedures – 2nd Edition"; July 2016 and Assay Migration Studies for In Vitro Diagnostic Devices – Guidance for Industry and FDA Staff.

4.0 DEFINITIONS

| Term or Abbreviation | Definition |
|--|--|
| ABCA GIRMS or ABCA2 GIRMS | Sercon's Automated Breath Carbon Analyzer Gas Isotope Ratio Mass Spectrometer, used to analyze stable isotopes of carbon in breath samples |
| ATE | Allowable Total Error |
| Bias | Difference between the expectation of the test results and an accepted reference value; estimate of a systematic measurement error |
| Delta values ($\delta^{13}\text{C}$) | The ratio of $^{13}\text{CO}_2/^{12}\text{CO}_2$ in each breath specimen as measured by GIRMS unites permil (‰) |
| DOB | Delta Over Baseline i.e. the difference in delta value at any given time point and the pre-meal/baseline delta value |
| GEBT | Gastric Emptying Breath Test |
| Measurand | Quantity intended to be measured |
| NCR | Nonconformance Report |
| SOP | Standard Operating Procedure |
| TAE | Total Analytical Error |
| QA | Quality Assurance |
| QC | Quality Control |

5.0 TRAINING REQUIREMENTS

Operators conducting this validation must be qualified according to the position requirements and must be successfully trained in the validation protocol and all analytical method SOPs/documentation associated with execution of this protocol. Training shall be documented, and training records maintained in accordance with Cairn's requirements stated in SOP-QA-007, Training System.

6.0 EQUIPMENT/MATERIALS

A complete list of all equipment and instrumentation required for execution of this protocol is provided in attached analytical procedures SOP-QC-017, Operation, Calibration and Maintenance – ABCA GIRMS and SOP-QC-090, Operation, Calibration and Maintenance – ABCA2 GIRMS. A list of major equipment/materials is provided in Table 1 below.

Information regarding test materials and reference materials will be recorded at the time of testing and documented in the validation report.

Table 1. List of Equipment/Materials

| Equipment Description | Manufacturer/Vendor | Model Number/Comments |
|-----------------------|---------------------|---|
| ABCA GIRMS | Europa Scientific | ABCA-A |
| ABCA2 GIRMS | Sercon Limited | ABCA-C/ABCA-D |
| Exetainer Tubes | Labco Limited | 438W/NP (white cap) 438B/NP (blue cap) |
| Monoject Tubes | Covidien/McKesson | 8881301710/48992 |

7.0 PROCEDURES

7.1 Validation Requirements

Determine bias and total analytical error using delta over baseline (DOB) values, i.e. differences in delta values ($\delta^{13}\text{C}$) of breath samples collected at any given timepoint and the baseline/pre-meal breath delta value) obtained by the ABCA GIRMS systems (original ABCA GIRMS and two new ABCA2 GIRMS systems. DOB values are used together with patient demographic information to calculate kPCD values. kPCD is the metric used to describe gastric emptying rates and make diagnostic decisions (refer to PRO-QC-202, ABCA2 GIRMS Clinical Performance Measures for determining diagnostic equivalence between the ABCA GIRMS instruments). DOB values are direct measures of ABCA GIRMS instruments' output (kPCDs include patient demographic information which would confound the analysis) and therefore DOBs are used to determine instrument bias/total analytical error.

PRO-CD-044, ABCA2 GIRMS Clinical Performance Measures – Patient Sample Collection, describes the collection of patient samples for clinical performance measuring studies, under an IRB approved protocol. Collect a minimum of seventy-five (75) sets of breath samples and conduct clinical performance measures experiments according to PRO-QC-202, ABCA2 GIRMS Clinical Performance Measures, by analyzing patient breath samples on the ABCA GIRMS system first and then on the ABCA2 GIRMS systems (ABCA-C or ABCA-D), then a third time on the ABCA2 GIRMS system on which the samples have not yet been analyzed.

7.1.1 Bias

Perform Bias calculations according to CLSI guidance EP09c and FDA's Guidance, Assay Migration Studies for In Vitro Diagnostic Devices. Refer to section 8 for a description of the statistical analysis of the data.

7.1.2 Total Analytical Error

Perform Total Analytical Error calculations according to CLSI guidance EP21 and FDA's Guidance, Assay Migration Studies for In Vitro Diagnostic Devices. Refer to section 8 for a description of the statistical analysis of the data.

Table 2. Bias and Total Analytical Error Acceptance Criteria

| Description | Justification |
|---|--|
| The Bias in DOBs on ABCA2-GIRMS should not exceed $\pm 0.5\%$ from the results from ABCA-A. | Previously approved instrument accuracy/bias requirements and manufacturer's specification for accuracy of ABCA-GIRMS. |
| Total Analytical Error in DOBs shall not exceed 30%. | Based on biologic variability data used to calculate a total allowable error (ATE) goal. |

For justification of these acceptance criteria see REP-QC-018, Validation Criteria for ABCA-GIRMS systems

7.2 General Procedures

See PRO-QC-202.00 ABCA2-GIRMS Clinical Performance Measures, Section 7.2 for a description of general procedures for collecting data to be used in this study.

8.0 STATISTICAL ANALYSIS

8.1 Bias Comparison

Compare bias in patient samples according to EP09c – Third Edition Measurement Procedure Comparison Bias Estimation Using Patient Samples.

- Calculate the difference in DOBs, between the candidate method (ABCA-C or ABCA-D) to the comparative method (ABCA-A).
- Calculate the mean difference and the standard error (calculated by dividing the standard deviation by the square root of the number of samples) of the difference.
- Calculate the 95% confidence interval and compare results to the acceptable limit of $\pm 0.5\%$ DOBs. If the interval is within this acceptance limit the results are deemed acceptable.

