8.0 STATISTICAL ANALYSIS

8.1 Clinical Diagnostic Agreement

8.1.1 Determine the diagnosis at individual time points for each subject on each instrument as follows:

- Positive for gastroparesis: kPCD below the reference range cut-off point (Table 4) for the applicable time point
- Negative for gastroparesis: kPCD above the reference range cut-off point (Table 4) for the applicable time point

Table 4. Reference Range Cut-Off Points for ¹³C-Spirulina GEBT

| Timepoint | 45 min | 90 min | 120 min | 150 min | 180 min | 240 min |
|---|--------|--------|---------|---------|---------|---------|
| Reference Range COP (kPCD min ⁻¹) | 12.9 | 26.9 | 34.4 | 39.5 | 43.0 | 35.0 |

8.1.2 Determine an overall diagnosis for each subject on each instrument using the following algorithm:

- Positive for gastroparesis if two out of three of the 90-, 120-, 150-timepoints are below the reference range cutoff point (Table 4) OR T_{max} (maximum kPCD value) occurs at the 240-minute timepoint.

Note: this algorithm is not an FDA approved algorithm for determining diagnosis by GEBT but is a convenient means of consistently determining an overall diagnosis that is supported by the interpretative guidelines published in the FDA approved labeling.

8.1.3 Determine the percent agreement in diagnosis between the comparative method (original ABCA-GIRMS) and the candidate method (new ABCA2-GIRMS) at each time point and for the overall diagnosis according to CLSI Guideline EP12-A2:

Prepare a contingency table (see Table 5) showing agreement between diagnoses between the comparative and candidate methods and each time point and for the overall diagnosis.

Table 5. Example contingency table for calculating percent agreement

| Candidate Method | Comparative Method | | |
|------------------|--------------------|----------|-------|
| | Positive | Negative | Total |
| Positive | a | b | a+b |
| Negative | c | d | c+d |
| Total | a+c | b+d | n |

Calculate overall percent agreement, percent positive agreement and percent negative agreement as follows:

- Overall percent agreement = $100 \times (a+d)/n$
- Percent positive agreement = $100 \times a/(a+c)$
- Percent negative agreement = $100 \times d/(b+d)$

8.1.4 Determine the 95% confidence intervals for the agreement measures according to CLSI Guideline EP12-A2 section 10.2.2.

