8.3 Total Analytical Error

Calculate Total Analytical Error (TAE) according to EP21 – Second Edition, Evaluation of Total Analytical Error for Quantitative Medical Laboratory Measurement Procedures. Use DOBs obtained during PRO-QC-202 – ABCA2-GIRMS Clinical Performance Measures. Calculate TAE by comparing DOB results from the original ABCA GIRMS system to DOB results from the two new ABCA2 GIRMS system.

- Determine the TAE estimate using a total of 75 patients with 8 breath samples collected for each patient (2 pre-meal samples, a 45, 90, 120, 150, 180 and 240-minute timepoints). Obtain appropriate DOB values for each patient and use these values to calculate the total analytical error.
- To calculate the TAE first calculate the difference value (d_i) by subtracting the DOB results from ABCA-A from the DOB results from the comparative method (either ABCA-C or ABCA-D).

$$d_i = \text{Candidate}_i - \frac{\sum_{j=1}^R \text{Comparative}_{i,j}}{R}$$

Where j is the replicate value from 1 to R for the ith patient (i = 1 to n)

Express d_i as a percent:

$$\%d_i = \frac{d_i}{\sum_{j=1}^R \text{Comparative}_{i,j}} * 100$$

Sort all $\%d_i$ from lowest to highest and calculate the Low and High Rank Positions to determine the TAE limits.

For 95%:

$$\text{Low Rank Position} = 0.5 + n * 0.025$$

$$\text{High Rank Position} = 0.5 + n * 0.975$$

Using these positions, find the $\%d_i$. If the rank position is nonintegral, interpolate the % difference from the values bracketing the rank position.

If the low TAE limit is greater than or equal to 30% and the high TAE limit is less than or equal to 30% then the minimum performance goal has been met.

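### Exhibit C 8.1 has no patient term in the bias standard error, so if all DOB differences are pooled its 95% interval is too narrow for a bias roughly constant over time

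*Combined protocol and SAP*

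**What the plan says.** Exhibit C 8.1 opens with "Compare bias in patient samples according to EP09c". It takes candidate-minus-ABCA-A differences in DOB, their mean, and a standard error "calculated by dividing the standard deviation by the square root of the number of samples". The decision rule is: "If the interval is within this acceptance limit the results are deemed acceptable". The limit comes from Table 2 in 7.1.2 ("The Bias in DOBs on ABCA2-GIRMS should not exceed" ±0.5, printed with a percent sign).

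Section 8.1 does not define a sample, split by timepoint or mention the patient. The nearby text points in different directions:

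- Exhibit C 7.1 calls the patient-level units sets: "Collect a minimum of seventy-five (75) sets of breath samples". Section 8.3 uses the word for single tubes: "using a total of 75 patients with 8 breath samples collected for each patient". Both usages point away from n = 75.
- The formula in 8.3 counts n over patients: "Where j is the replicate value from 1 to R for the ith patient (i = 1 to n"). Exhibit B 8.1.3 compares the methods at each time point. Both point towards n = 75.
- Exhibit C 8.2 fits a regression to the same DOBs with patient ID as a random effect and has its own acceptance sentence.

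Exhibit C 4.0 defines DOB as a timepoint's delta value minus the pre-meal value. Protocol 6.1 schedules six post-meal timepoints and two pre-meal tubes. The documents do not say whether the two tubes are averaged.

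**The concern.** Section 8.1 describes one mean and one standard error for all DOB differences of an instrument, so pooling 450 values is the natural reading. Those values come from only 75 patients. Within a patient, all six DOBs on one instrument subtract the same pre-meal reading, so the error in that reading enters all six differences with the same sign. Dividing by √450 treats them as independent.

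Section 8.1 is the only bias rule that compares a confidence interval with the limit; the acceptance sentence in 8.2 compares the bias itself. If the 8.1 interval is too narrow, an instrument whose true bias is at the limit passes 8.1 more often than a 95% interval implies. The results support a PMA supplement covering both new instruments.

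**Working it through.** **Inputs from the documents.** 75 patients minimum, up to 120 (Protocol 5.0); 6 DOBs per patient per instrument, so 75 × 6 = 450 (or 120 × 6 = 720); a 95% interval; limit 0.5. The plan gives no standard error, SD or correlation to reproduce.

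**Assumptions.** The limit is read as 0.5 absolute DOB units. Reading errors are independent, and the bias is constant over timepoints. Post-meal error variance is k times baseline variance, and b baseline tubes are averaged.

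**Correlation.** The difference at time t is d = (post_C − pre_C) − (post_A − pre_A). Two timepoints of one patient share only the baseline terms, so ρ = (1/b)/((1/b) + k) = 1/(1 + kb).

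**Effect on the pooled interval.**

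- Design effect: D = 1 + (6 − 1)ρ; the standard error is too small by a factor of √D.
- True coverage: 2Φ(1.96/√D) − 1.
- Acceptance by 8.1 at a true bias on the limit: Φ(−1.96/√D). With a correct standard error this is Φ(−1.96) = 2.5%.

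| Case | ρ | D | √D | Coverage | Acceptance at limit |
|---|---|---|---|---|---|
| k = 1, b = 1 | 0.50 | 3.50 | 1.87 | 70.5% | 14.7% |
| k = 1, b = 2 | 0.33 | 2.67 | 1.63 | 77.0% | 11.5% |
| k = 4, b = 1 | 0.20 | 2.00 | 1.41 | 83.4% | 8.3% |
| k = 4, b = 2 | 0.11 | 1.56 | 1.25 | 88.4% | 5.8% |

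Outside this range, ρ = 0.05 gives coverage of 92.0% and acceptance of 4.0%. ρ = 0.7, which would need other patient-level error such as run day, gives 64.4% and 17.8%.

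**Simulation of 8.1 alone** (75 × 6, 20,000 runs per case, same order of cases). Pooled coverage was 0.700, 0.775, 0.833 and 0.884; acceptance at the limit was 0.150, 0.111, 0.085 and 0.060. An interval from 75 patient means had coverage of 0.949–0.952 and acceptance of 0.024–0.025.

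**Bias that varies by timepoint.** If its SD is f times the within-timepoint SD, the pooled variance grows by 1 + f² while the true variance of the mean does not, so the effective D becomes D/(1 + f²). The defect disappears at f = √(D − 1) = 1.58, 1.29, 1.00 and 0.75 in the four cases.

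**Effect on the decision** (assumed SD 0.5, 75 patients).

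- Pooled half-width: 1.96 × 0.5/√450 = 0.046.
- Patient-level half-width: t(74) × 0.5 × √(D/450), with t(74) = 1.9925, = 0.088, 0.077, 0.066 and 0.059.
- The verdict differs only if the observed mean lies in a band about 0.01 to 0.04 wide beside the limit. At ρ = 0.50 the largest passing mean falls from 0.5 − 0.046 = 0.454 to 0.5 − 0.088 = 0.412.
- With 120 patients the half-width goes from 0.037 to 0.046–0.069.
- Half-widths scale with the SD. At ρ = 0.50 and 75 patients, SD 0.2 gives 0.018 against 0.035, and SD 2 gives 0.185 against 0.351.

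**The case against.** **The unit is open.** What 8.1 shows for certain is an undefined word. With n = 75, or one analysis per timepoint, its formula is correct. A literal tube count would give 75 × 8 = 600, not 450. Section 8.1 also defers to EP09c, which is not in the documents and might define the unit. All of this stands, so the point is conditional. A reader might infer that the plan commits to an invalid interval; the text does not support that. But it leaves a natural reading that gives a wrong interval, and a citation does not settle the unit within the plan.

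**Section 8.2 is a second check.** A reader might take 6% to 15% as the plan's overall false-acceptance rate. It is not: it describes 8.1 alone. In a simulation of 8.1 and 8.2 together (1,500 runs, SD 0.5, true bias 0.5, an assumed DOB profile of about 5 to 17 with 30% between-patient spread, 8.2 estimates required inside 0.5 at all six listed DOB values), joint acceptance was about 11.5%, 7.5%, 4.9% and 3.9% in the four cases. With a patient-level 8.1 it was about 2% to 3%. Section 8.2 reduces the inflation but does not correct the 8.1 interval.

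**The size is assumed, and 2.5% is not a stated target.** Both are true. The documents state a 95% interval; 2.5% is only what that interval implies at the limit. Every magnitude depends on variance components that the documents do not give.

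**The practical effect is small.** At an assumed SD of 0.5, the band in which the verdict changes is at most about 0.042 wide (0.088 − 0.046), or 8% of the limit. This stands, and limits how much weight the point can bear.

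**Conclusion.** The concern holds in conditional form. If 8.1 pools the DOB differences and the bias is roughly constant over timepoints, its nominal 95% interval is too narrow because each patient's shared baseline error is ignored. For assumed correlations of 0.11 to 0.50, the standard error is understated 1.25- to 1.87-fold, coverage is about 88% to 70%, and 8.1 alone accepts a bias at the limit in about 6% to 15% of cases instead of 2.5%. Joint acceptance with 8.2 is lower, and bias that varies by timepoint can offset the defect or remove it.

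This does not show that an instrument would be wrongly accepted: when the observed bias is well inside the limit, both intervals give the same answer. It is worth correcting before analysis, because n = 75 and n = 450 give different intervals from the same data and the text does not choose. Confidence is medium, since the size rests wholly on assumptions.

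**What to change.** In Exhibit C 8.1, state that the patient is the unit of analysis, separately for ABCA-C and ABCA-D. Either average each patient's DOB differences and use SD/√(number of patients) with a t interval, or fit an intercept-only mixed model with a patient random effect. The model matches 8.2 and copes with a missing timepoint. Say whether the baseline is one pre-meal tube or the mean of the two, and give the unit of the limit. Keep the 0.5 limit and the interval rule.

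This takes two or three sentences and no extra data. The cost is a wider interval: for an assumed SD of 0.5 and 75 patients, a half-width of about 0.06 to 0.09 instead of 0.046 (about 0.10 if ρ were 0.7).

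Per-timepoint intervals may be reported descriptively. Requiring all six to pass is not part of this fix, because it is a materially stricter rule. In simulation with SD 0.5 and 75 patients, a true bias of 0.35, inside the limit, passed all six in about 19% to 37% of runs, against 92% to 100% for the patient-level interval.

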8.2 Method Comparison

Compare results from the two ABCA2 instruments (ABCA-C and ABCA-D) to the original ABCA (ABCA-A) by using a mixed effects regression model in which the DOB values of the ABCA2 machines are predicted using the ABCA DOB values.

The mixed effect model follows the model:

$$y = X\beta + Zu + \epsilon$$

Where:

- y is the known vector of DOB values from ABCA2 (DOB of ABCA-C/D values)
- X is a vector of the observations of the fixed effects (DOB A values)
- β is a vector of the fixed effects coefficients (DOB A values)
- Z is a vector of observations of the random effects (patient ID)
- u is a vector of random effects values (patient ID)
- ϵ is a vector of error values (residuals)

After the regression equation has been established, calculate the confidence intervals for slope and the intercept. Once the confidence intervals have been calculated, determine the Bias at the following DOB values:

| DOB |
|-----|
| 0 |
| 5 |
| 10 |
| 15 |
| 20 |
| 25 |

Once the bias has been calculated, compare the bias against the acceptance criteria. If the bias is less than the $\pm 0.5\%$ acceptance criterion then the comparison is considered acceptable.

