7.2 General Procedures

- 7.2.1 Accession and analyze breath samples according to SOP-CD-021, GEBT Breath Sample Accessioning and Chain of Custody and SOP-CD-005, Breath Test Processing.
- 7.2.2 Prepare QC standards and reference gases for this protocol according to SOP-QC-043, QC Gas Preparation for ABCA GIRMS.
- 7.2.3 Run the ABCA GIRMS and ABCA2 GIRMS systems according to SOP-QC-017, Operation, Calibration and Maintenance – ABCA GIRMS and SOP-QC-090, Operation, Calibration and Maintenance – ABCA2 GIRMS.
- 7.2.4 Analyze breath samples first on the original ABCA-GIRMS system and then on either the ABCA-C or ABCA-D ABCA2 GIRMS system. Analyze samples a third time on the ABCA2 GIRMS system on which the samples have not yet been analyzed. Note: the original ABCA-GIRMS system, ABCA-A utilizes a larger sample of breath (~4 mL) than the ABCA2-GIRMS systems (1-2 mL). For this reason, all samples will be analyzed on ABCA-A first. The order in which samples are analyzed on ABCA-C and ABCA-D will be randomized to minimize any bias cause by running the same samples on different instruments in the same order as outlined in Table 3.

Table 3. Randomization Table

| Subject Number | Study Participant Breath Sample Analysis Order | | |
|----------------|--|--------------------|--------------------|
| | ABCA GIRMS (A) | ABCA2 GIRMS (C) | ABCA2 GIRMS (D) |
| 001 | 1 | 2 | 3 |
| 002 | 1 | 3 | 2 |
| 003 | 1 | 3 | 2 |
| 004 | 1 | 2 | 3 |
| Etc | Etc | Etc | Etc |

- 7.2.5 Enter LAF, gas standards and subject breath sample delta values into the Linearity Adjustment Excel workbook according to SOP-QC-090 for samples analyzed on the ABCA2 GIRMS systems.
- 7.2.6 Enter Quality Control standards data on the appropriate QC charts which are located in the instrument laboratory. Verify that QC values are within accepted ranges according to SOP-QC-090. If QC data is outside the accepted ranges, initiate a nonconformance report (NCR) according to SOP-QA-014, Control and Handling of Nonconformances, to investigate a potential cause of the nonconformance.
- 7.2.7 Enter DOB and kPCD results for each patient on each instrument into a spreadsheet for analysis.

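### Exhibit C 8.2 regresses ABCA2 DOB on a single ABCA-A reading as if that reading had no error, so the slope comes out too flat and the bias at the ends of the DOB grid is distorted

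*Combined protocol and SAP*

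**What the plan says.** Exhibit C (PRO-QC-191), section 8.2, specifies a mixed effects regression "in which the DOB values of the ABCA2 machines are predicted using the ABCA DOB values". On the predictor side, "X is a vector of the observations of the fixed effects (DOB A values"). On the random side, "Z is a vector of observations of the random effects (patient ID"). The only other random term is the residual, which belongs to the ABCA2 reading.

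After the fit, the analyst is told to "determine the Bias at the following DOB values": 0, 5, 10, 15, 20 and 25. The decision follows: "Once the bias has been calculated, compare the bias against the acceptance criteria". The criterion is in Exhibit C, Table 2: "The Bias in DOBs on ABCA2-GIRMS should not exceed" plus or minus 0.5 relative to ABCA-A. It is printed with a percent sign. I read it as 0.5 DOB units, because section 8.1 sets the interval for the mean DOB difference against it.

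On replication, Exhibit B (PRO-QC-202), section 7.2.4, says: "Analyze breath samples first on the original ABCA-GIRMS system and then on either the ABCA-C or ABCA-D ABCA2 GIRMS system". It describes one pass on ABCA-A. The kit in protocol section 3.4, Table 1, holds six post-meal tubes for six timepoints, so there is one tube per timepoint, plus two pre-meal tubes. The total-error formula in Exhibit C 8.3 allows for R comparator replicates but never gives R, and 8.2 mentions no averaging.

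**The concern.** ABCA-A is the comparator, but it is still an instrument with measurement error. Each ABCA-A DOB is the difference of two measured deltas and carries error from both. When the predictor in a regression is measured with error, the fitted slope shrinks towards zero and the line tilts about the mean DOB. Two identical instruments then appear to differ, with ABCA2 reading high at low DOB and low at high DOB. A real proportional over-reading is partly hidden, and a real under-reading is exaggerated.

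The setting makes this more than a technicality. Section 8.1 tests only the average difference over all DOBs, so 8.2 is the bias check meant to find error that changes with DOB level. That is the check the tilt weakens.

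**Working it through.** **Inputs.** From the documents: 75 patients with 6 post-meal DOBs each, so 75 x 6 = 450 pairs per ABCA2 instrument; the DOB grid 0 to 25; the limit of 0.5. Not in the documents, so assumed: the SD of instrument error in one tube reading (s), and the mean (m) and SD of true DOB. The plan states no slope or power figure for 8.2, so there is none to reproduce.

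**Step 1: formula.** Let the true relation be ABCA2 = b x true DOB, and let k = Var(true) / (Var(true) + Var(ABCA-A error)). The fitted slope is then b x k, and the estimated bias at DOB x is

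(b - 1)x - b(1 - k)(x - m).

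For identical instruments (b = 1) this reduces to (1 - k)(m - x). It is positive below the mean, negative above it, and largest at whichever end of the grid is farthest from m.

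**Step 2: numbers in.** Take m = 12.5, true DOB SD 5 (variance 25), and error variance 2s² because a DOB uses two readings. A true over-reading of 2.4% gives a bias of 0.024 x 25 = 0.60 at DOB 25.

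| s | Error variance | 1 - k | Identical: -(1 - k) x 12.5 | True 2.4%: 0.60 - 1.024(1 - k) x 12.5 |
|---|---|---|---|---|
| 0.1 | 0.02 | 0.02/25.02 = 0.0008 | -0.01 | 0.59 |
| 0.3 | 0.18 | 0.18/25.18 = 0.0071 | -0.09 | 0.51 |
| 0.5 | 0.50 | 0.50/25.50 = 0.0196 | -0.25 | 0.35 |

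At s = 0.3 the expected estimate falls from 0.60 to about the limit, so the verdict becomes close to a coin toss.

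**Step 3: simulation of the model in the plan.** The set-up was a REML random-intercept model, 75 x 6 DOBs, curves proportional to the cut-offs in Exhibit B Table 4, peak DOB mean 14 and SD 4, and baseline error shared within patient. A pass requires all six absolute biases below 0.5. Ranges show the spread over repeat runs. The corrected fits allow for ABCA-A error, with equal error on both instruments.

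| s | Identical: bias at DOB 0 / DOB 25 | True 2.4% passes, plan | True 2.4% passes, corrected |
|---|---|---|---|
| 0.1 | +0.01 / -0.01 | 1% | 0% |
| 0.2 | +0.04 / -0.05 | 23% | 8% |
| 0.3 | +0.06 to +0.08 / -0.09 to -0.11 | 46% to 57% | 12% to 25% |
| 0.5 | +0.20 to +0.21 / -0.26 to -0.29 | 83% to 87% | 28% to 29% |

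Identical instruments fail falsely in 9% to 12% of data sets at s = 0.5. Averaging the two baseline tubes changes little (51% against 16% at s = 0.3). With peak mean 10 instead of 14, the plan passes 82% of over-reading instruments at s = 0.3, against 25% after correction.

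**Step 4: when the artefact alone reaches 0.5.** With m = 12.5 this needs 1 - k = 0.5/12.5 = 0.04, so error SD = true SD x √(0.04/0.96). For true DOB SDs of 3, 4, 5, 6 and 7.2 that is an ABCA-A DOB error SD of 0.61, 0.82, 1.02, 1.22 and 1.47. If 0.5 is read as a 95% limit on one delta (an assumption), s is about 0.25 and the DOB error SD about 0.36. The artefact is then 0.03, 0.06 and 0.18 at each end for true SDs of 7.2, 5 and 3.

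**Step 5: why 8.1 does not cover this.** At mean DOB 12.5, a 2.4% over-reading gives a mean difference of 0.024 x 12.5 = 0.30, inside the limit. The mean DOB would have to reach 0.5/0.024 = 20.8 before the average difference touched 0.5. In simulation 8.1 passed this instrument 96% to 100% of the time.

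**Step 6: does an errors-in-variables fit remove the artefact?** In a second set-up (mean DOB 12.5, total SD about 5.6, identical instruments, s from 0.1 to 1.0), the plan's model gave +0.008 / -0.007 at s = 0.1, rising to +0.521 / -0.559 at s = 1.0. Deming regression with an error ratio of 1 kept the slope between 0.997 and 1.000, the bias at DOB 0 between -0.002 and +0.014, and the bias at DOB 25 between -0.053 and +0.005.

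**The case against.** The strongest reply is that this is a small effect seen through chosen inputs. For s of 0.1 to 0.3, identical instruments show at most about 0.11 of artefact against 0.5, with no false failures. False failures appear at s = 0.5, which is large for an instrument whose accuracy specification is itself cited as 0.5. The 2.4% example lies close to the limit: its bias at DOB 20 is 0.024 x 20 = 0.48, which is acceptable. Under the assumed distribution about 0.05% of DOBs exceed 25 and under 2% exceed 20, so the failing point is an extrapolation. At a 3% over-reading the plan's regression passes only 0% at s = 0.2 and 6% at s = 0.3. The criteria also rest on REP-QC-018, which is not included. All of this stands, and it limits the point to instruments near the limit. It does not remove the point, because the artefact adds to any real bias and the plan itself chose to judge bias at DOB 25.

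A reader might infer that the patient random effect makes the dilution worse. It does not here: it absorbs baseline error shared by a patient's six DOBs. Without it, ordinary least squares gives about +0.25 / -0.33 to +0.26 / -0.36 at s = 0.5, larger than the plan's model. It reduces the artefact without correcting it.

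A reader might also infer that DOB 0 and 25 are always the two worst points, or the only ones tested. All six are tested. With mean DOB 8, DOB 25 is 17 units from the mean and DOB 20 is 12, both farther than DOB 0 at 8.

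**Conclusion.** The point holds, with a size that depends on quantities the documents do not give. The model in 8.2 has no error term for a once-measured comparator, the direction of the resulting distortion is certain, and it falls on the bias check meant to detect level-dependent bias. The artefact at DOB 25 runs from about -0.01 (per-tube SD 0.1) through about -0.1 (0.3) to -0.26 to -0.29 (0.5). These figures assume 75 x 6 DOBs, peak DOB mean 14 and SD 4, and equal error on both instruments. It is negligible for a precise instrument, and for a moderately imprecise one it can decide the result near the limit.

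A reader might go further and conclude that the plan's pass or fail result will be wrong. The documents do not support that: the instrument SD and DOB spread are unknown, and for the artefact alone to reach 0.5 the ABCA-A DOB error SD must be roughly 0.6 to 1.5 (mean DOB 12.5). A changed verdict is possible, not shown.

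**What to change.** Replace the regression in Exhibit C 8.2 with an errors-in-variables fit, such as Deming regression. Use the ABCA-A to ABCA2 error-variance ratio, on the DOB scale, from the precision study described in protocol section 3.5 (PRO-CD-039), which recorded DOB values on both instrument types. Resample whole patients in a bootstrap to respect clustering. Compute the bias at DOB 0, 5, 10, 15, 20 and 25 from that fit, and state the ABCA-A DOB imprecision and the ratio used.

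Do not substitute a regression of the difference on the mean unless the precision data show similar error on both instruments. Protocol section 11.0 and Exhibit B 7.2.4 give different breath volumes (about 4 mL against 1 to 2 mL), so equal error cannot be presumed. With identical calibration and per-tube SDs of 0.2 on ABCA-A and 0.5 on ABCA2, that method gives about -0.08 to -0.09 at DOB 0 and +0.12 to +0.13 at DOB 25, worse than the plan's +0.04 / -0.04.

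The cost is a change of wording and of one model, slightly wider uncertainty, and reliance on an error ratio that is itself estimated. No new samples or measurements are needed.
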